5.6. Subject Withdrawal/Discontinuation

Any subject who discontinues from the study treatment for any reason will have his or her study treatment discontinuation recorded.

A subject may discontinue study treatment during the Main Treatment Period; however the subject should still remain as a study participant for scheduled visits through Month 3 (Visit 5). The subject should complete the subsequent 30-day Follow-Up Visit (Visit 9) regardless of whether they stop all anticoagulant therapy or are placed on a treatment that they were not assigned to at randomization.

If a subject discontinues from treatment after Month 3 he/she will be discontinued from the study and should still receive a Discontinuation Visit and a 30-day Follow-Up Visit.

5.6.1. Discontinuation from Treatment within the Main Treatment Period (Month 3)

Early discontinuation of study drug is discouraged. However if, in the Investigator's opinion, continuation of study drug would be detrimental to the subject's well-being or in specific clinical situations (eg, liver function test [LFT] disturbances, severe renal insufficiency, TE, bleeding), the study drug can be stopped permanently.

Subjects who discontinue treatment during the Main Treatment Period should return to the clinical site per the study procedure schedule (Table 17.1) for all remaining safety and efficacy assessments through the Month 3 visit (Visit 5) regardless of what treatment, if any, they may subsequently be taking. A 30-day Follow-Up Visit (Visit 9) will be required. A telephone call for Follow-Up assessment may be conducted in exceptional circumstances when the subject is not able or willing to present to the clinical site.

The reasons for discontinuation from treatment must be documented.

If a subject discontinues treatment prior to Month 3, the Investigator will complete and report the observations as thoroughly as possible at scheduled visits including the date of last treatment and the reason for discontinuation from study treatment though 3 months of observation.

5.6.2. Discontinuation from Treatment and Study beyond Month 3 up to Month 12

During the Extension Period (beyond 3 months treatment), all subjects who discontinue from the study treatment will also discontinue from the study and will return to the clinical site for a Discontinuation Visit (Visit 8) and a 30-day Follow-Up Visit (Visit 9) after the Discontinuation Visit.

Note: Subjects in the Extension Period do not need to be followed through 12 months of study procedures and can discontinue from treatment and study per Investigator discretion at any time with a Discontinuation Visit after Month 3 and a 30-day Follow-Up Visit after the Discontinuation Visit.

5.6.3. Reasons for Discontinuation from Study Treatment

Subjects may **discontinue the treatment** for any of the following reasons:

Proprietary and Confidential Page 66

- 1. End of requirement for anticoagulant therapy
- 2. Reasons related to adverse events (AEs):
 - If initiating or continuing study drug places the subject at undue hazard as determined by the Investigator;
 - If the subject had a serious adverse event (SAE) or other safety concern that is related to study drug treatment as determined by the Investigator;
 - If the subject had a major bleeding event as determined by the Investigator;
 - If the subject has an aggravation or new occurrence of renal insufficiency with estimated eGFR <30% of normal for age and size (Cockcroft-Gault equation for pediatric subjects ≥12 years of age and modified Schwartz equation for pediatric subjects <12 years of age);
 - If the subject demonstrates hepatic test abnormalities including:

Elevation of alanine transaminase (ALT) and/or aspartate transaminase (AST) \geq 3 × ULN and TBL \geq 2 × ULN simultaneously.

ALT and/or AST $\ge 8 \times$ ULN requires an immediate interruption of study drug treatment and prompt repeat testing to confirm abnormality.

- If the subject demonstrates clinical jaundice that requires an immediate interruption of study drug treatment and prompt repeat testing to confirm abnormality;
- If the subject has any elevation of transaminases combined with clinical symptoms of liver injury;
- If a subject discontinues study drug due to confirmed liver enzyme abnormalities or jaundice. The subject will have additional evaluations at the discretion of the Investigator as follows:

Hepatitis A, B, C, and E screening (anti-HAV IgM, HBsAg, anti-HCV plus viral titer, and evaluation for Hep E);

Abdominal ultrasound;

Antinuclear antibody (ANA) and anti-SmAb;

Cytomegalovirus (CMV);

Epstein-Barr virus (EBV);

Additional evaluations as deemed appropriate by the Investigator to exclude other causes of liver enzyme and TBL elevations.

Subjec t's follow-up will be required on a weekly basis until the values (transaminases and TBL) return to a clinically acceptable level. For the above laboratory blood tests, using the central laboratory is recommended. However, if circumstances warrant the use of a local laboratory, copies of the local laboratory results will be required. All clinically significant hepatic enzyme abnormalities and/or hepatic events are to be documented in the eCRF with prompt submission of the adjudication dossier for events that led to study drug discontinuation or were reported as

SAEs where no alternative etiology has been found after work-up and where causal relationship to study drug cannot be ruled out.

- 3. Unplanned cardiac surgery due to aggravation of cardiac conditions;
- 4. Pregnancy;
- 5. Study terminated by Sponsor;
- 6. Protocol violation;
- 7. Lack of efficacy.

Those subjects whose participation extended beyond Month 3 (Visit 5) will have study procedures terminated at the time of discontinuation from treatment and study with a Discontinuation Visit (Section 6.5.3).

If the subject discontinued study treatment due to an AE, the Investigator will follow the subject until the AE has been clinically stabilized.

5.6.4. Reasons for Withdrawal at any Time during the Study

Withdrawal of a subject will only occur, by definition, if no additional protocol scheduled visit or Follow-Up Visit is possible. The definition of withdrawal is appropriate for those cases that occur in the Main Treatment Period because of the requirement to continue subjects on scheduled visits even if they discontinue treatment prior to Month 3 (Visit 5). If a subject withdraws after Month 3 this would be classified as a discontinuation from treatment and study.

Any subject who is withdrawn from the study treatment for any reason will have their reasons for withdrawal records.

Subjects may be withdrawn from the study after signing the informed consent form (ICF) during the Main Treatment Period for the following reasons:

- Withdrawal of subject consent by subject or legal guardian(s)
- Death
- Lost to follow-up (attempts should be made to not have any subject lost to follow-up)
- AE that occurs during the Main Treatment Period that requires withdrawal.

5.6.5. Withdrawal Procedures

If a subject is withdrawn from the study, the Investigator will complete and report the observations as thoroughly as possible up to the date of withdrawal including the date of last treatment and the reason for withdrawal. Subjects who withdraw from the study during the 3 month Main Treatment Period will also have a 3 month Follow-Up phone call to ascertain any events (TE and/or bleeding events) that may have occurred since withdrawal. The timeframe for the 3-month Follow-Up phone call assessment is from the date of subject randomization.

5.6.6. Procedures for Discontinuation from Treatment or Study; or Withdrawal from Study

In accordance with the Declaration of Helsinki and other applicable regulations, a subject has the right to discontinue study treatment or withdraw consent for participation in the study at any time and for any reason without prejudice to his or her future medical care by the physician or at the institution.

While subjects are encouraged to complete all study evaluations, they may discontinue study treatment, discontinue from study, or withdraw from the study at any time and for any reason without penalty. Every effort will be made to determine why any subject discontinues study treatment, or study, or withdraws from the study prematurely. This information should be recorded.

The most likely reasons for withdrawal are death, lost to follow-up or withdrawal of consent, or an AE in which case all subsequent visits will NOT be possible as stated in the protocol.

All subjects who classify as discontinue from the study treatment or study with an ongoing AE must be followed until the event is deemed resolved or clinically stable even if they are not willing to participate in the study any longer. If a subject discontinues study or withdraws after dosing, all data normally collected prior to study discharge should be collected at the time of discontinuation from study or withdrawal, or at the scheduled visit of the study.

In case of withdrawal, a genuine effort must be made to determine the reason(s) why a subject fails to return for the necessary visits. If the subject is unreachable by telephone, a registered letter, at the minimum, should be sent to the subject requesting him/her to contact the clinical site.

If a subject is withdrawn or discontinued from study treatment or study, the IXRS will be called by the clinical site to register the subject status.

Please see suggested classification of discontinuation and withdrawal status in Table 5.2.

	Discontinue Treatment	Discontinue Study	Withdrawal
Randomization through Month 3	Eligible	Not Eligible (Need to follow through Month 3 with Follow-Up Visit)	Eligible (Assumes no additional visit is possible, 3-month Follow-Up phone call attempted from date of randomization)
Beyond Month 3 through Month 12	Eligible	Eligible (A Discontinuation Study Visit will be conducted with Follow-Up Visit)	Not Eligible (Unless NO Discontinuation Visit is possible, in which case a phone call will be attempted)

Table 5.2:Classification of Discontinuation and Withdrawal Status for Subjects by
Scheduled Visit

5.6.7. Follow-Up Procedures.

Subjects who complete the Main Treatment Period (Month 3) but do not continue into the Extension Period, will have a their Month 3 Visit and a Follow-Up Visit 30 days after last dose of study drug and discontinued from the study. Follow-Up Visits may be conducted by phone, however, if the subject experienced an adverse event of concern (Serious) or an endpoint event since their Discontinuation Visit, an office visit is highly recommended.

Subjects who discontinue treatment from the Main Treatment Period prior to Month 3 will continue to be followed monthly according to the Schedule of Events (Appendix 17.1) through the Month 3 visit (Visit 5), and have a 30-day Follow-Up Visit. If treatment discontinuation occurs prior to Month 2 visit, the 30-day Follow-Up Visit will occur on the same day as the Month 3 visit.

Subjects who extend toward 12 months of study treatment and decide to no longer participate will have a subsequent 30-day Follow-Up Visit after their Discontinuation Visit.

5.6.7.1. Temporary Interruption of Study Drug

If a subject's treatment with study drug must be interrupted for medical or surgical reasons (eg, hospital admission for an invasive procedure, a major medical condition, surgery, thrombocytopenia due to cytotoxic medication, or dental work); use of a prohibited concomitant medication; or other reasons (eg, temporary situation that prevents subject adherence with the study drug administration schedule, etc), the subject's study drug should be resumed as early as the situation allows. Edoxaban should be discontinued for 24 hours prior to the initiation of the procedures (depending on PK/PD data in children). Subjects should be encouraged to restart study drug after an interruption except when absolutely contraindicated. The duration of study drug interruption can vary depending upon the individual circumstances, and study drug may be resumed regardless of the duration of time that it had been interrupted. Any subject who temporarily interrupts study drug will have the reason recorded in the eCRF.

5.6.8. Subject Re-screening Procedures

Re-screening (retesting of laboratory test results) is permitted only once for any subject with Sponsor approval who failed to meet eligibility criteria upon initial screening related to a specific inclusion/exclusion criteria. If a subject needs to be rescreened for any particular time-dependent module (ie, laboratory, vital signs, etc.) the Investigator will perform an unscheduled visit within **30 days of the original screening visit** and the appropriate module will be used to accommodate new data that would make the subject eligible to be randomized. The subject identification number will remain the same at the time of re-screening. The initial screening information and the reason why the subject is ineligible for the initial evaluation will be uploaded into the electronic data capture (EDC) system.

Re-screening (re-testing of laboratory results) of a subject may occur only once. If there is a failure to meet study entry criteria the failed subject will be recorded in the Screening Log and EDC.

6. STUDY PROCEDURES

Potential subjects will have the study risks and possible benefits explained, the ICF reviewed, and all questions answered for them. Subjects will undergo procedures specific to study qualification (Section 6.2) only after the ICF is signed by the subject/or the subject's legal representative, and age appropriate assent obtained from subjects capable of doing so. Subjects who complete the screening period and are determined to be eligible for study participation per the inclusion and exclusion criteria will be randomized in a 2:1 ratio to either the edoxabantreatment arm or the SOC-treatment arm, respectively, for the first 3 months of the study, after which all subjects will be offered edoxaban at the appropriate dose for age and weight at the time of informed consent

All subjects will undergo evaluation for safety and efficacy evaluations at the EOT at Month 3 with a 30-day Follow-Up. Subjects who discontinue treatment prior to Month 3 will continue with the scheduled visits up to Month 3 with the 30-day Follow-Up. Subjects who participate in the Extension Period will undergo safety and efficacy endpoint evaluations (bleeding events, TE, or any other AEs) at Months 6, 9, and 12, and 30-days after cessation of treatment if treatment up to 12 months is required. If treatment discontinuation occurs prior to Month 2 visit, the 30-day Follow-Up Visit will occur on the same day as the Month 3 visit.

Subjects will return to the clinical site on a monthly basis to receive study therapy even if there are no scheduled procedures. This process will ensure subject compliance and accountability for distribution/return of study drug. However, in cases where access to the clinical sites cannot occur monthly after Month 3, accommodations will be made to distribute up to 3 months of study drug to match the 3-month visit schedule.

All suspected bleeding and TE endpoints as well as hepatic abnormalities identified by the Investigator will be adjudicated by the blinded CEC. Adjudication packages will contain appropriate diagnostic tests, clinic notes, laboratory tests, discharge summaries, autopsy reports, etc used in the subject work-up following a suspected event.

6.1. Note Concerning Echocardiogram

All subjects will have an echocardiogram at study screening to rule out asymptomatic thrombosis. Subjects with evidence of symptomatic venous or arterial thrombosis during study screening period are not permitted in the study. Valid echocardiograms are images taken within 5 weeks prior to Randomization Visit.

A follow-up echocardiogram will be taken at Month 3 to ascertain asymptomatic thrombosis. **IF** there is a symptomatic thrombosis prior to Month 3 which would represent a thrombotic event, it should be documented by the appropriate imaging procedure. A Month 3 echocardiogram will NO LONGER be necessary at Month 3 visit if a symptomatic event was experienced by the subject and was documented by an appropriate image.

In the Extension Period after Month 3, any symptomatic event will be documented and a recommended image captured to support the event. The Month 12 echocardiogram will be optional in all circumstances.

A Month 3 echocardiogram is optional if the subject experiences a symptomatic TE documented by an image. A reported post-Month 3 symptomatic TE should have a supporting appropriate

Proprietary and Confidential Page 71 image. If no symptomatic TE is reported during the Extension Period, the Investigator has the option to perform an echocardiogram at his/her discretion to rule out any asymptomatic TE at study discontinuation.

The Schedule of Events for this study is provided in Appendix 17.1.

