2.1.2. Secondary Objectives

2.1.2.1. Key Secondary Objectives

The key secondary objectives are:

- To compare the efficacy of edoxaban against SOC with regard to the development of symptomatic thromboembolic events (TE) in the systemic arterial or venous pathways including deep vein thrombosis (DVT), pulmonary embolism (PE), stroke, intracardiac thrombus, systemic embolic event (SEE), myocardial infarction (MI), and asymptomatic intracardiac thrombus identified by cardiac imaging occurring from randomization to Month 3 Visit.
- To compare the safety of edoxaban against SOC with regard to all bleedings which occur in the Main Treatment Period: from the date of first dose of study drug to Month 3 Visit, or to the date of last dose of study drug plus 3 days if study treatment is discontinued, whichever is earlier.
- To compare the efficacy of edoxaban against SOC with regard to death as a result of a TE occurring from randomization to Month 3 Visit
- To compare edoxaban against SOC with regard to all-cause mortality from randomization to Month 3 Visit.
- To assess the safety of edoxaban with regard to the combination of major and CRNM bleedings occurring during the Extension Period (from Month 3 Visit to last dose plus 30 days).
- To assess the efficacy of edoxaban with regard to the development of symptomatic TE or asymptomatic intracardiac thrombus identified by cardiac imaging occurring during the Extension Period.
- To assess the safety of edoxaban with regard to all bleedings occurring during the Extension Period.
- To assess the efficacy of edoxaban with regard to death as a result of a TE occurring during the Extension Period.

- To assess the efficacy of edoxaban with regard to all-cause mortality occurring during the Extension Period.
- To evaluate the population pharmacokinetics and pharmacodynamics of edoxaban in relation to the efficacy and safety endpoints in subjects with cardiac conditions at risk of TE.

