2.3.3. Secondary Efficacy Endpoints

The secondary efficacy endpoints are:

- The combination of symptomatic TE in the systemic arterial or venous pathways including DVT, PE, stroke, intracardiac thrombus, SEE, and MI, and asymptomatic intracardiac thrombus identified by cardiac imaging, that occur from randomization to the Month 3 Visit.
- Deaths as a result of TE that occurs from randomization to the Month 3 Visit.
- All-cause mortality from randomization to the Month 3 Visit.
- The combination of symptomatic TE in the systemic arterial or venous pathways and asymptomatic intracardiac thrombus identified by cardiac imaging, which occur from the day after the Month 3 Visit to the date of the last dose of study drug plus 30 days for subjects who participate in the Extension Period.
- Deaths as a result of TE that occurs from the day after Month 3 Visit to the date of the last dose of study drug plus 30 days for subjects who participate in the Extension Period.
- All-cause mortality from the day after the Month 3 Visit to the date of the last dose of study drug plus 30 days for subjects who participate in the Extension Period.

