6.5.1. Month 6 (Visit 6) Procedures

- Record concomitant medications
- Count unused study drug tablets/bottles to assess compliance
- Dispense study drug medication and review dosing instructions
- Perform physical examination (Section 9.9) including:

Vital signs (BP, heart rate, and body temperature after resting in a sitting or supine position [Note: the appropriate cuff size base on arm circumference will be used.])

Height and body weight (may be performed by an Investigator or other healthcare provider designated by the Investigator).

- Urine pregnancy test for females of child bearing potential
- Review for symptomatic endpoint events (bleeding, symptomatic TE with appropriate imaging)
- Safety review for AEs/SAEs
- Collect blood samples for the following laboratory tests:

Serum creatinine test

eGFR assessment

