6.5.2. Month 9 (Visit 7) Procedures

- Record concomitant medications
- Count unused study drug tablets/bottles and calculate compliance
- Dispense study drug medication and review dosing instructions
- Perform physical examination (Section 9.9) including:

Vital signs (BP, heart rate, and body temperature after resting in a sitting or supine position [Note: the appropriate cuff size base on arm circumference will be used.]

Height and body weight (may be performed by an Investigator or other healthcare provider designated by the Investigator).

- Urine pregnancy test for females of child bearing potential
- Review for symptomatic endpoint events (bleeding and TE)
- Safety review for AEs/SAEs
- Collect blood samples for the following laboratory tests:
 - Serum creatinine

eGFR assessment

6.5.3. Month 12/Discontinuation Visit (Visit 8; Appropriate for subjects completing Month 12 or treated beyond Month 3 and discontinuing study prior to Month 12)

Discontinuation from study visit will only be required for those extended into the study beyond Month 3 because all subjects are to have study procedures through Month 3.

Procedures for subjects who withdraw consent from the study or are discontinued from the study treatment for any reason are discussed in Section 5.6.

All randomized subjects extended beyond Month 3 who wish to discontinue treatment and study will have Discontinuation Visit (Visit 8) performed when the last dose of study drug is administered after Month 3.

The following will be performed at this visit:

- Record concomitant medications
- Count unused study drug tablets/bottles and calculate compliance
- Perform physical examination (Section 9.9) including:

Vital signs (BP, heart rate, and body temperature after resting in a sitting or supine position [Note: the appropriate cuff size base on arm circumference will be used.])

- Safety review for AEs/SAEs
- Review for symptomatic endpoint events (bleeding and TE)
- Collect blood samples for the following laboratory tests:

LFTs (ALT, AST, TBL, and ALP)

Serum creatinine

eGFR assessment

Hematology

- Urine pregnancy test for females of child-bearing potential
- Optional echocardiogram to evaluate presence of asymptomatic intracardiac thrombosis based on Investigator's discretion.

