11.4.1.1. Secondary Efficacy Analysis

The TE stated in this Section, include symptomatic thrombi in the systemic arterial or venous pathways (DVT, PE, stroke, SEE, intracardiac thrombus, and MI), and asymptomatic intracardiac thrombus identified by cardiac imaging.

The following secondary efficacy endpoints will be summarized by treatment group using incidence, and annualized event rate for both the Main Treatment Period and the Extension Period, as well the rate difference between edoxaban and the comparator with the corresponding 95% CI for the Main Treatment Period. The incidence of each component will also be summarized by treatment group. This analysis will be based on CEC adjudicated results.

- The combination of symptomatic TE in the systemic arterial or venous pathways including DVT, PE, stroke, SEE, intracardiac thrombus, MI, and asymptomatic intracardiac thrombus identified by cardiac imaging that occur from randomization to the Month 3 Visit.
- Deaths as a result of TE that occurs from randomization to the Month 3 Visit.
- All-cause mortality occurring from randomization to the Month 3 Visit.
- The combination of symptomatic TE in the systemic arterial or venous pathways including DVT, PE, stroke, SEE, intracardiac thrombus, and MI, and asymptomatic intracardiac thrombus identified by cardiac imaging, which occur from the day after the Month 3 Visit to the date of last dose of study drug plus 30 days for subjects who participate in the Extension Period.
- Deaths as a result of TE that occurs from the day after the Month 3 Visit to the date of last dose of study drug plus 30 days for subjects who participate in the Extension Period.
- All-cause mortality which occur from the day after the Month 3 Visit to the date of last dose of study drug plus 30 days for subjects who participate in the Extension Period.

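### The Extension TE rate counts silent intracardiac thrombus but requires no imaging to find it, so the composite is a lower bound and is not on the same footing as the Main Treatment Period composite

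*Combined protocol and SAP*

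**What the plan says.** **Endpoint.** Section 2.1.2.1 lists among the key secondary objectives the "development of symptomatic TE or asymptomatic intracardiac thrombus identified by cardiac imaging occurring during the Extension Period". Section 2.3.3 defines the matching endpoint as symptomatic TE together with "asymptomatic intracardiac thrombus identified by cardiac imaging, which occur from the day after the Month 3 Visit to the date of the last dose"; the window closes 30 days after that dose.

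**Imaging.** The only Extension echocardiogram is at Month 12 or discontinuation. Section 6.1 states "The Month 12 echocardiogram will be optional in all circumstances" and adds that, where no symptomatic TE has been reported, "the Investigator has the option to perform an echocardiogram at his/her discretion to rule out any asymptomatic TE at study discontinuation". Section 6.5.3 (the Visit 8 list) agrees: "Optional echocardiogram to evaluate presence of asymptomatic intracardiac thrombosis based on Investigator's discretion". Table 17.1 and its footnote j say the same. At Month 6 the endpoint check is "Review for symptomatic endpoint events (bleeding, symptomatic TE with appropriate imaging"; the Month 9 list is similar, and neither includes an echocardiogram. The 30-day Follow-Up Visit (Section 6.6) may be by phone and covers symptomatic events only. By contrast, Sections 6.1 and 6.4.4 schedule a Month 3 echocardiogram for everyone except subjects with an imaged symptomatic TE.

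**Analysis.** Section 11.4.1.1 says "The following secondary efficacy endpoints will be summarized by treatment group using incidence, and annualized event rate", for both periods, with each component's incidence also shown. Section 11.1 bases Extension analyses on participants who take only edoxaban in that period. It does not restrict them to imaged subjects, and in general it does not impute missing data.

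**The concern.** An asymptomatic thrombus enters the data only if someone images the child. In the Extension that choice is the investigator's, subject by subject. A participant who is not imaged cannot contribute an asymptomatic event but stays in the population over which the rate is taken. The reported rate then mixes thrombus risk with imaging practice, and the plan reports nothing that would let a reader separate them.

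What is at stake is interpretation. The randomized comparison ends at Month 3, so the Extension supplies the longer-term efficacy data. Section 11.4.1.1 lists the Main and Extension composites in one set, with the same components and the same incidence and annualized-rate statistics. A lower Extension rate could be read as sustained efficacy when part of the drop is reduced ascertainment. The same composite recurs in the exploratory Extension analysis of Section 11.4.1.2.

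**Working it through.** **The plan's own figures.** The plan states no Extension TE rate, imaging uptake or asymptomatic share. Its one precision figure (Section 11.6) concerns bleeding: (0.085 − 0.103) ± 1.96 × √(0.085 × 0.915/100 + 0.103 × 0.897/50) gives −11.84% to 8.24%, matching the stated −11.8% to 8.2%. It does not bear on this point.

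**Direction.** Let s be the symptomatic TE risk, a the asymptomatic thrombus risk, and c the share of asymptomatic thrombi that are imaged.

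- True composite = s + a.
- Reported composite = s + a × c.
- Reported minus true = −a × (1 − c), which is never positive and is zero only if a = 0 or c = 1.

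**Size if imaging is unrelated to risk.** Then c = f, the share of subjects imaged. With q = a/(s + a), the asymptomatic share of true TEs, the share of TEs missed is q × (1 − f). Both q and f are assumptions.

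| q | f = 10% | f = 30% | f = 60% |
|---|---|---|---|
| 20% | 18% | 14% | 8% |
| 50% | 45% | 35% | 20% |
| 80% | 72% | 56% | 32% |

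**Size if imaging is selective.** If imaged subjects have k times the thrombus risk of unimaged subjects, c = f × k/(f × k + 1 − f). Take k from 0.5 to 4 (assumed).

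- f = 10%: c runs from 0.05/0.95 = 5.3% to 0.4/1.3 = 30.8%. The share missed runs from 0.2 × 0.692 = 14% to 0.8 × 0.947 = 76%.
- f = 60%: c runs from 0.3/0.7 = 42.9% to 2.4/2.8 = 85.7%. The share missed runs from 0.2 × 0.143 = 3% to 0.8 × 0.571 = 46%.
- On the rate scale, with s = 1% and a = 2% (true composite 3.0%) and f from 25% to 75%, c runs from 14% to 92% and the reported rate from about 1.3% to 2.8%.

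**Would a rate among imaged subjects repair it?** Not by itself. The imaged-only risk divided by the true risk is k/(f × k + 1 − f). Over f = 25% to 75% and k = 0.5 to 4 this runs from 0.5/0.875 = 0.57 to 4/1.75 = 2.29.

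**The case against.** Four points can be made for the plan.

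- **No comparison is planned.** Section 6.4 confines treatment comparisons to the Main Treatment Period, and Section 11.4.1.1 gives rate differences only there. The intra-patient and historical-control comparisons also use Main Period results. This stands. A reader might infer that the plan contrasts the two composites, or that a randomized result is biased; the documents support neither.
- **Components are reported.** This stands in part. Component incidence would let a reader approximate a symptomatic-only figure, for which all Extension edoxaban participants are the right denominator. It gives no symptomatic-only annualized rate and no number imaged.
- **The SAP may deal with it.** Section 11.7 leaves missing-data handling to a SAP. No text available here addresses unimaged Extension subjects. That they count as thrombus-free is an inference from Sections 11.1 and 11.4.1.1, though the natural one.
- **The size is unknown.** This stands. A reader might settle on one figure, such as the 45%, 35% and 20% missed when half of TEs are silent. Those values rest on a single assumed share and on imaging unrelated to risk, which investigator discretion gives no reason to expect.

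A reader might also expect the corrected lead figure to look worse for edoxaban. It cannot: a symptomatic-only rate is equal to or below the composite.

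**Conclusion.** The point holds as one about ascertainment and labelling of a descriptive, single-group secondary endpoint. The Extension composite is a lower bound on the rate it names, and it does not match the Main Period composite, which has a scheduled echocardiogram. Under the stated assumptions the share of TEs missed is 18% to 72% at 10% uptake and 8% to 32% at 60%. With selective imaging the ranges become 14% to 76% and 3% to 46%. These figures illustrate; they do not estimate.

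The conclusion rests on three things: unimaged participants stay in the denominator as non-events; at least one silent thrombus occurs and is missed; and what an Extension image shows arose after Month 3. Investigator discretion makes selection plausible, but the documents do not say in which direction. The primary safety endpoint and the randomized comparisons are untouched.

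**What to change.** Amend Section 11.4.1.1, before the SAP is finalized, for the Extension Period only. No change to the imaging schedule is proposed.

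1. Lead with symptomatic TE: incidence and annualized rate over all Extension participants taking only edoxaban, labelled symptomatic-only.
2. Report asymptomatic intracardiac thrombus separately as n/N among subjects with any Extension cardiac imaging, since Section 7.1 prefers echocardiography but accepts other cross-sectional modalities. Label it descriptive and open to selection. Give the number and baseline characteristics of imaged and unimaged subjects. Add a sensitivity range for the unimaged, for example with their risk set from zero to twice that of imaged subjects; the upper end matches k = 0.5 above.
3. If the composite is kept, label it a lower bound and state that it is not comparable with the Main Treatment Period composite. Apply the same labels to the exploratory Extension composite in Section 11.4.1.2.

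The cost is a few extra tables and a check that the eCRF records Extension imaging with negative findings as well as positive ones. The drawback is that the lead figure will be equal to or lower than the composite, so without its label it could itself be read as better efficacy.
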